1.2. Study Design

The study is a prospective, single arm, multicenter efficacy study, consisting of 60 subjects who will complete the study (note: if any patients are lost to follow-up or withdrawn, enrollment will increase to compensate for loss of these subjects). The subjects will receive up to 16 RD1 applications. In case of complete healing, subject will be called for one confirmatory visit two weeks later or before discharge from the SNF (the earlier of the two). Subject data will be kept in each site's records.

All diabetic subjects' glycemic management will be performed by a qualified physician. All subjects will have wound care specialist or wound surgeon or dermatologist involved in their wound care

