8. PREMATURE WITHDRAWAL OF SUBJECTS

Subjects have the right to withdraw from the study at any time for any reason. The investigator also has the right to withdraw a subject from the study, if he/she seems it to be in the subject's best interest. It is recognized that an excessive rate of withdrawals may render the study uninterrupted and, therefore, it is desirable to avoid unnecessary withdrawals.

While lack of venous access is not anticipated as a major problem, a subject will be withdrawn from the trial if the investigator cannot find venous access during the treatment study visits (Visits 1-16).

Noncompliance with study treatment/ offloading in a manner that interrupt treatment and delay healing, according to principal investigator judgment

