9. LOST TO FOLLOW-UP

Subjects who are lost to follow-up will be included in the primary safety analysis but only patients who complete the study will be included in the secondary objectives analysis; where wound area data are missing, imputation using LOCF (last observation carried forward) will be used.

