13. DATA ANALYSIS

13.1. Study Population and Sample size

- 13.1.1 The safety population will be all subjects who receive at least one RD1 treatment.
- 13.1.2 The intent-to-treat population (ITT) will be all subjects who complete the study.
- 13.1.3 Sample size is initially set as 60 but enrollment will be increased if necessary to compensate for drop-outs so that 60 patients complete the trial.

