13.2.1. Primary Endpoint

Efficacy- The performance of RD1 in terms of wound progress towards closure in wounds deemed suitable for treatment with RD1 (ITT population)

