13.2.2. Secondary Endpoints

- Safety - Determine complication rates for all adverse events compromising serious adverse events, adverse events (AEs), and device-related adverse events (DRAEs); AEs include any lack of venous access events (ITT and Safety Population)
- Efficacy - Assess the incidence of complete wound closure at 16 weeks for wounds treated with RD1 (defined as skin re-epithelialization without drainage or dressing requirements) (ITT population).
- Efficacy - Assess the wound Percent Area Reduction (PAR) (ITT population)
- Efficacy- Assess the optimal duration between applications of RD1 per wound parameter (ITT population)
- Efficacy- Assess the need of design and procedure improvements of the RD1 for specialized nursing facilities (SNF) (ITT population)
- Sub Group Analysis – asses the safety and efficacy per wound etiology (subgroup of ITT population)
- Asses the cost of RD1 procedure in SNF compared to cost of treatment before RD1 (ITT population)
- Assess wound pain compared to wound pain during treatment before RD1 (ITT population)
- Assess medical staff wound related weekly labor of wound treatment before and during RD1. (ITT population)

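### The protocol labels a completers-only set ITT and bases the primary and every efficacy endpoint on it, so early leavers, some of them withdrawn for wound worsening, vanish from the denominator.

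*Protocol*

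**What the plan says.** Section 13.1 of the protocol defines two sets. The safety population (13.1.1) is everyone who received at least one RD1 treatment. For the other, 13.1.2 states: "The intent-to-treat population (ITT) will be all subjects who complete the study".

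This second set carries the efficacy results. Section 13.2.1 gives the primary endpoint as "The performance of RD1 in terms of wound progress towards closure in wounds deemed suitable for treatment with RD1 (ITT population"). Section 13.2.2 attaches the same set to complete closure at 16 weeks, to percent area reduction ("Assess the wound Percent Area Reduction (PAR) (ITT population")) and to the remaining efficacy, cost, pain and labour endpoints. The etiology subgroups are drawn from it. Only the safety endpoint also uses the safety population.

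Leavers are replaced. Section 1.2 states: "if any patients are lost to follow-up or withdrawn, enrollment will increase to compensate for loss of these subjects". Section 13.1.3 states: "enrollment will be increased if necessary to compensate for drop-outs so that 60 patients complete the trial".

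Section 9 says that "only patients who complete the study will be included in the secondary objectives analysis" and continues in the same sentence: "where wound area data are missing, imputation using LOCF (last observation carried forward) will be used".

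**The concern.** An intent-to-treat set keeps subjects whether or not they finish. This one keeps them only if they finish, and here finishing is not independent of how the wound does. Leavers are removed and refilled, so failures can disappear from the denominator.

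In a single-arm study the closure rate and the percent area reduction are themselves the result, and no control group shares the bias. Reported under the ITT label, they would suggest that early failures had been counted when they had not.

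**Working it through.** **Step 1. Does leaving depend on the wound?**

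- Appendix 11: a subject whose wound exposes bone, or can be probed to bone, is withdrawn. Explicit.
- Appendix 5: a wound that grows by at least 50% in area, or rises in grade, is reviewed centrally to decide on withdrawal. Conditional.
- Section 8, under the withdrawal heading: "Noncompliance with study treatment/ offloading in a manner that interrupt treatment and delay healing, according to principal investigator judgment". This concerns behaviour, but it is tied to delayed healing and rests on judgment.
- Sections 4.1.1, 4.1.3 and 4.1.5 (infection, deterioration, necrosis) are individual stopping rules. Exit from the study is only an inference: they do not say the subject leaves, and 4.1.1 allows treatment to resume.

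**Step 2. Is the set symmetric for healed and unhealed subjects?** A healed subject finishes at a confirmatory visit two weeks after healing, or earlier at discharge (1.4). An unhealed subject must stay to week 16 (1.6.3.4). Withdrawal for lost venous access (Section 8) and for missed visits (Section 6) applies during treatment. Most healed subjects are therefore exposed to drop-out for less time. The exception is a subject who heals in weeks 15 or 16 and waits the full two weeks.

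**Step 3. Does Section 9 repair this?** No. Its LOCF clause shares a sentence with the completers-only rule, so as written it fills gaps within completers. If it was meant for leavers, Section 9 and 13.1.2 conflict. Section 9 also refers to a primary safety analysis, although the primary objective is efficacy. It does not govern the primary endpoint, which becomes completer-only through 13.1.2 and 13.2.1.

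**Step 4. Size for closure.** The protocol has no figure to reproduce here: it states 60 completers but no drop-out rate, closure rate or sample size calculation. All rates below are assumed.

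*(a) Leavers counted as not closed.* Closure among all treated = completer rate × (1 − p), where p is the share lost. With 36/60 = 60%:

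- p = 10%: 0.60 × 0.90 = 54%
- p = 20%: 0.60 × 0.80 = 48%

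An extreme case uses the 25% study stopping rule in 4.3. If deterioration were the only reason for exit, the largest number treated with 60 completers and fewer than 25% lost is 79: 19/79 = 24.1%, whereas 20/80 = 25.0% meets the rule. Closure is then 36/79 = 45.6%. This assumes that every deteriorated ulcer leaves, one ulcer per subject, and all treated as the denominator, which 4.3 does not state.

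*(b) Drop-out unrelated to the wound, true closure 50% at 16 weeks.* Constant weekly hazards: h = ln 2 / 16 = 0.0433 for healing and d for drop-out, with w weeks from healing to the confirmatory visit.

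- Healed completers: H = h/(h+d) × (1 − e^(−16(h+d))) × e^(−dw)
- Unhealed completers: U = e^(−16(h+d))
- Share lost: 1 − H − U, with d solved to give each total
- Completer closure: H/(H+U)

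Example, w = 2 and 10% lost: d = 0.0085, H = 0.463, U = 0.437, so closure = 0.463/0.900 = 51.5%.

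| Share lost | w = 0 | w = 1 | w = 2 |
|---|---|---|---|
| 10% | 52.1% | 51.8% | 51.5% |
| 15% | 53.2% | 52.8% | 52.3% |
| 20% | 54.5% | 53.8% | 53.2% |
| 25% | 55.9% | 55.0% | 54.2% |

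If the same leavers count as not closed, the rate among all treated is H: 46.3–46.9% at 10% lost and 40.6–41.9% at 25% (w = 2 to w = 0).

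**The case against.** The definition and its assignment are current text and cannot be read another way, so the real objections concern extent and remedy.

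- **Exit on outcome is thinly documented.** Wound-status withdrawal is explicit only in Appendix 11 and conditional in Appendix 5, completing the study is not defined, and 1.6.3.4 gives week-16 and early-termination subjects the same visit. This stands as a limit on size. It does not rescue the set: 13.1.3 contrasts completers with drop-outs, and 1.2 speaks of replacing lost subjects.
- **The 36/79 case stacks assumptions.** It does, and should be read only as a constructed extreme.
- **Counting leavers as failures can miss by more than the defect does.** True under model (b). At 25% lost, completers err by +4.2 to +5.9 points and the failure rule by −8.1 to −9.4. At 10% lost the figures are +1.5 to +2.1 and −3.1 to −3.7. Exits unrelated to the wound are plausible here, such as referral to another facility (7.4). The text compels the all-treated denominator and the correct name. The failure rule is a conservative choice and must be labelled so.
- **Requiring confirmed closure adds to the endpoint wording**, which mentions only re-epithelialization without drainage or dressings. The confirmatory visit in 1.4 and the reassessment in Appendix 5 support the requirement, but the endpoint text should then say so.
- **The SAP may define other sets.** It was not available. A true ITT set there would contradict 13.1.2, so the protocol needs correcting either way.

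**Conclusion.** The concern holds and must be fixed. The protocol fixes a completer set, names it ITT, and uses it for the primary and all efficacy endpoints while replacing those who leave. The bias is likely to favour RD1. Its size cannot be determined from the document.

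The figures above concern closure only and rest on assumed closure and drop-out rates. They suggest a gain of roughly 1.5 to 6 points over a true 50% when drop-out of 10–25% is unrelated to the wound. The gap reaches 6 to 12 points (60% against 54% or 48%) at 10–20% drop-out if every leaver is a failure. None of them measures bias in the primary endpoint, because this document gives wound progress towards closure no metric.

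**What to change.** - **13.1.2:** define the efficacy set as all subjects with at least one RD1 application, which is the existing safety population. Stop calling completers ITT.
- **Section 9:** remove the completers-only restriction for efficacy.
- **1.2 and 13.1.3:** extra enrolment may continue, but replaced subjects stay in the analysis.
- **Closure at 16 weeks:** count early leavers without confirmed closure as not closed, say that this is conservative, and align the endpoint wording on confirmation. Record the reason for each exit, and leave a time-to-closure sensitivity analysis by reason to the SAP.
- **Percent area reduction:** use the Early Termination area where it exists, otherwise the Section 9 LOCF, applied to all treated subjects.
- **Completers:** define what completing the study means, and keep this set as a supportive analysis under its own name.

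The cost is protocol wording, with the SAP aligned to it. No new wound measurement is needed: the Early Termination visit already records size and depth, and subjects truly lost have their last visit. No clinical rule changes. The drawback is a less favourable closure rate, which can err low when drop-out is unrelated to the wound.

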13.2. Statistical Analyses

Please refer to the SAP (statistical analysis plan) for full details.

13.2.1. Primary Endpoint

Efficacy- The performance of RD1 in terms of wound progress towards closure in wounds deemed suitable for treatment with RD1 (ITT population)

13.2.2. Secondary Endpoints

- Safety - Determine complication rates for all adverse events compromising serious adverse events, adverse events (AEs), and device-related adverse events (DRAEs); AEs include any lack of venous access events (ITT and Safety Population)
- Efficacy - Assess the incidence of complete wound closure at 16 weeks for wounds treated with RD1 (defined as skin re-epithelialization without drainage or dressing requirements) (ITT population).
- Efficacy - Assess the wound Percent Area Reduction (PAR) (ITT population)
- Efficacy- Assess the optimal duration between applications of RD1 per wound parameter (ITT population)
- Efficacy- Assess the need of design and procedure improvements of the RD1 for specialized nursing facilities (SNF) (ITT population)
- Sub Group Analysis – asses the safety and efficacy per wound etiology (subgroup of ITT population)
- Asses the cost of RD1 procedure in SNF compared to cost of treatment before RD1 (ITT population)
- Assess wound pain compared to wound pain during treatment before RD1 (ITT population)
- Assess medical staff wound related weekly labor of wound treatment before and during RD1. (ITT population)

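### Safety by wound etiology is assigned to completers only, so treated subjects withdrawn for harm drop out of those rates; Section 9 adds a wording conflict

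*Protocol*

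**What the plan says.** **Analysis sets (Section 13.1).** Item 13.1.1 defines the safety set: "The safety population will be all subjects who receive at least one RD1 treatment". Item 13.1.2 then sets out a second, narrower group in these terms: "The intent-to-treat population (ITT) will be all subjects who complete the study". The set labelled ITT is thus a completer set. Sections 1.2 and 13.1.3 replace drop-outs until 60 subjects complete.

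**Endpoints (Section 13.2.2).** The overall safety bullet carries both sets: "AEs include any lack of venous access events (ITT and Safety Population"). The etiology bullet carries one: "asses the safety and efficacy per wound etiology (subgroup of ITT population").

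**Objectives (Section 1.1).** The only primary objective is efficacy. Safety is secondary objective 1, and safety and efficacy by etiology is secondary objective 6.

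**Lost subjects (Section 9).** Lost subjects are "included in the primary safety analysis but only patients who complete the study will be included in the secondary objectives analysis".

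**Who fails to complete.** Section 4.1 stops individuals for uncontrolled infection, failed venipuncture with loss of venous access, ulcer deterioration, health deterioration (including hospitalisation) and substantial necrotic tissue. Section 8 adds that "a subject will be withdrawn from the trial if the investigator cannot find venous access during the treatment study visits (Visits 1-16"). Appendix 11 withdraws subjects whose wound exposes bone or can be probed to it.

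**The concern.** The etiology analysis covers both efficacy and safety but has one population label, and that label is the completer set. For safety this selects on the outcome: several of the reasons for leaving the study are themselves adverse events in the protocol's own terms. Lack of venous access is counted as an AE (1.1, 13.2.2), infection soon after application is an example of a device-related event (7.2), and a rise in wound stage or a sudden increase in area or depth is an anticipated AE (7.3). A subject withdrawn for one of these is removed from both numerator and denominator, and replacement up to 60 completers makes the loss invisible in the denominator.

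The stake is a stated purpose of the trial. The Introduction says the protocol should be enough to establish the safety of RD1 across wounds of different etiologies. The analysis that addresses this question directly is the one confined to completers.

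The population is not a detail left open for the SAP. The protocol fixes it, and fixes it to the wrong set.

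**Working it through.** **1. Tracing the sets**

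| Analysis | Set named in 13.2.2 | Who is in it (13.1) | Withdrawn treated subjects included? |
|---|---|---|---|
| Overall AE, SAE and DRAE rates | Safety Population | at least one RD1 treatment | yes |
| Overall AE, SAE and DRAE rates | ITT | completers | no |
| Safety per etiology | ITT subgroup | completers in that etiology | no |

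The third row is the only one without an all-treated version.

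**2. Section 9 against Section 1.1**

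- First half of the sentence: "Subjects who are lost to follow-up will be included in the primary safety analysis".
- Second half: "only patients who complete the study will be included in the secondary objectives analysis".
- Section 1.1 has no primary safety objective; safety is secondary objective 1, and safety by etiology is secondary objective 6.

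Read literally, the first half refers to an analysis that does not exist, and the second half confines every safety analysis to completers. The inclusion clause also mentions only subjects lost to follow-up, not those withdrawn under Sections 4.1 or 8. The last-observation rule in the same sentence concerns wound area and restores no adverse events.

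**3. Direction of the bias**

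In one etiology let n be the completers, m of them with a given harm, and d the treated non-completers, k of them with that harm.

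- Completer rate: m/n
- All-treated rate: (m + k)/(n + d)
- The all-treated rate is higher exactly when k/d > m/n, that is, when the harm is more frequent among non-completers. This is expected for a harm that leads to withdrawal.
- If every non-completer had the harm (d = k), the gap is k(n − m)/[n(n + k)].

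**4. Size, by illustration**

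The protocol gives no event rates, no drop-out rate and no split by etiology. Assumptions: n = 15, from an equal split of the 60 completers over the four etiologies named in the Introduction (60/4 = 15); m = 0; d = k, from 1 to 4. Intervals are exact (Clopper-Pearson) 95%.

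| k withdrawn for the harm | Completers | All treated |
|---|---|---|
| 1 | 0/15 = 0% (0 to 21.8) | 1/16 = 6.3% (0.2 to 30.2) |
| 2 | 0/15 = 0% (0 to 21.8) | 2/17 = 11.8% (1.5 to 36.4) |
| 3 | 0/15 = 0% (0 to 21.8) | 3/18 = 16.7% (3.6 to 41.4) |
| 4 | 0/15 = 0% (0 to 21.8) | 4/19 = 21.1% (6.1 to 45.6) |

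With some harm among completers the bias remains, but the completer rate is no longer zero. For m = 2 and k = 3, completers give 2/15 = 13.3% and all treated (2 + 3)/(15 + 3) = 5/18 = 27.8%. The gap is 3 × 13/(15 × 18) = 14.4 percentage points.

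The sample size of 60 cannot be re-derived from the protocol, and the point does not depend on it.

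**The case against.** **The overall safety result is intact.** A reader might infer that subjects stopped for harm vanish from the trial's safety results altogether. The documents do not support this. The venipuncture stopping rule (item 4.2.3) shows why. It acts at 25%, so with 60 completers and no other drop-outs up to 19 such drop-outs could occur without a stop: 19/79 = 24.1%, whereas 20/80 = 25.0% reaches the bound. Setting 0/60 in completers against 19/79 looks striking, but 13.2.2 already plans the overall rate in the Safety Population, so if those 19 had been treated, 19/79 would be reported. This objection stands. The defect is confined to the per-etiology rates and to the redundant completer version of the overall rates.

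**Lost venous access is not device harm in the protocol's terms.** Section 7.2 expressly leaves lack of venous access out of the device-related examples; it is an ordinary AE. Section 8 does not expect it to be a major problem, and the exclusion criteria remove subjects from whom blood cannot be drawn. This stands too: it is one adverse event among several, not the main case.

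**Completer rates need not be zero.** Completing the study is not defined. Section 4.1.1 lets treatment be interrupted for cellulitis or local infection and resumed, and Section 7.4 allows resumption in some cases after referral elsewhere. Bleeding, allergic reaction and high pain (7.2) are not individual stopping rules. A reader might infer a zero rate by construction for every serious harm; that holds only for events that actually end participation.

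**Section 9 can be read sensibly.** Its sentence contrasts safety with the other objectives, and 13.2.2 largely settles the overall rates. It is therefore a mislabel to correct, not a second loss of data.

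**Events can still be tabulated.** AEs are recorded at each visit whatever the analysis set, so a per-etiology table in all treated subjects could be produced. That is true, but the protocol as written does not plan it.

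**Conclusion.** The point holds in limited form. Followed as written, Section 13.2.2 yields per-etiology safety rates from completers only, with no all-treated counterpart. For harms that lead to withdrawal these rates are biased downward. In the overall safety endpoint only the completer version shares the bias, and the Safety Population version is sound.

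The size is unknown. The illustrated gap of 6.3 to 21.1 percentage points in one etiology rests on an assumed 15 completers, 1 to 4 subjects withdrawn for the harm, no such harm among completers and no other non-completers. The intervals are wide and overlap, so the argument rests on who is excluded, not on a demonstrated difference. The direction rests on the harm being more common among non-completers than completers.

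The conflict in Section 9 is real in the text but secondary. It should be corrected so that its completer clause cannot be used to justify the wrong set for safety.

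**What to change.** **Section 13.2.2, etiology bullet.** Separate the two parts and assign the safety part to the Safety Population, by etiology.

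**Section 13.2.2, overall safety bullet.** Make the Safety Population the analysis set. Drop ITT there, or label the completer version supportive.

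**Section 9.** Replace the reference to a primary safety analysis with safety analyses (Safety Population), and limit the completer clause to the non-safety objectives.

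**Cost.** Protocol wording only, with matching text in the SAP where needed. No extra subjects, visits or data are required. The per-etiology adverse event rates may become less favourable; the overall Safety Population rate does not change.

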14. REGULATORY OBLIGATIONS

14.1 Sponsor's Obligations

The sponsor will assume the following responsibilities:

1. Provide the investigator with the necessary information—protocol and device user's manual or instructions for use (also incorporated into the Investigator Brochure).
2. Inform the Investigator of all new information that may affect his/her decision of whether to continue participation in the study.
3. Provide supplies for the investigation.

The sponsor will maintain the following records:

1. A signed protocol and CRF
2. All correspondence that relates to the clinical trial
3. Signed investigator agreements
4. Records of device shipment and disposal (shipping receipts, material destruction records, etc.)
5. Other records as required by the Health Authority.

14.2 Investigator's Obligations

Clinical research studies are subject to the regulations of the regulatory authority of the country. Upon signing the protocol, the investigator agrees to assume the following responsibilities and to keep the required records for a period of 2 years after the last approval of marketing application and until there are no pending or contemplated marketing

applications, or at least 2 years have elapsed since the formal discontinuation of clinical development of the investigational product, and to file the required reports in a timely manner:

1. Conduct the investigation in compliance with the protocol. Changes to the protocol may only be made after approval by the investigation team and the Ethical Committee (IRB/EC), or when necessary to protect the safety, rights, or welfare of a subject.
2. Personally conduct or supervise the investigation.
3. Read and understand the information in the Protocol and Investigator Brochure.
4. Be aware of the potential risks and side effects of the investigational device.
5. Ensure that all associates, colleagues, and employees assisting in the conduct of the study are informed of their obligations.
6. Inform all subjects that the device is being used for investigational purposes and ensure that the requirements related to obtaining the informed consent are met.
7. Dispose of or return remaining supplies as directed by the sponsor.

Maintain the following records (for the period of time as specified above):

1. Signed copy of the protocol
2. Signed consent forms
3. All correspondence relating to the clinical trial
4. Case Report Forms.

File the following reports:

1. Serious unexpected adverse DRAE reports received by the sponsor.
2. Regular SAE reports produced by the PI.
3. Deviations made from the protocol for emergency use, must be reported to the sponsor as soon as possible, but no later than five working days after occurrence.

